- b. Are certain test procedures and stimuli particularly sensitive to the deficits found with this population of veterans and are deficit patterns influenced by the coexistence of PTSD?
- c. Does the addition of background noise produce over-additive effects in this population of veterans and does PTSD increase the effect?
- d. Does this population of veterans perceive and demonstrate benefit when fitted with hearing aids that provide mild high-frequency gain and does PTSD influence benefit?
- e. Is hearing aid benefit predictable by measures of auditory processing, speech perception, psychoacoustic, verbal working memory, and language processing? Furthermore, does the coexistence of PTSD influence the relationship between these measures and hearing aid benefit?

Expected Outcomes

- a. This population of veterans will differ from veterans with no history of blast exposure, and the presence of PTSD will increase severity and alter the deficit pattern.
- b. This population of veterans will experience significant problems with the addition of background noise and the effect will be influenced by linguistic load, verbal working memory and attention.
- c. This population of veterans will demonstrate and perceive benefit from being fitted with mild-gain high-frequency hearing aids, although the coexistence of PTSD will restrict perceived benefit.
- d. Mild-gain high-frequency amplification will improve speech perception skills in quiet and noise, and improve linguistic processing and executive function.
- e. Benefit from amplification will relate to the deficits that the veterans present.

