Using the order in which participants complete Part 2 as an identifier, the participants from the mTBI-only and mTBI+PTSD groups will be randomly assigned to receive either treatment or delayed treatment, and then ranked in random order for participation in Part 2. Each of the groups will be populated using this selection procedure. The assignments will be determined at the onset of the study by the PI with subsequent replacement as needed. Because Part 2 is preliminary in nature (not a randomized control trial) and includes low numbers of participants, any participants opting out of Part 2 will be replaced using the rank ordered list. Participants will be informed at the conclusion of Part 1 whether they can enroll in Part 2. If participants do not qualify, they will be informed that they could be contacted at a later date to act as a replacement. The study staff will be responsible for discussing enrollment in Part 2 with participants.

Payment

The veteran participants will be paid \$50 per session (laboratory and home visits) for their participation, and a \$25 travel allowance for each session requiring travel to one of the testing sites. They will be paid through the preferred method at each site (e.g., Financial Management System, vouchers, payment cards). When the Financial Management System is used the payment will not be immediate. The significant others who complete the HHIA-SO will not receive any payment.

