Primary Analyses – Basic descriptive statistics will be computed and examination of statistical assumptions will be performed for all study measurements. For questionnaire data, analysis of variance (ANOVA) or Kruskal Wallis test will be used to determine differences in the overall and subset scores between the mTBI groups. The analysis will also include basic descriptive statistics for behavioral data test measures at baseline and at 6 months for the mTBI-only and mTBI+PTSD groups, and at baseline and 12 months for the delayed-treatment groups. We will focus on the changes in the behavioral test measures from baseline to 6 months (mTBI-only and mTBI+PTSD treatment groups) and from baseline to 12 months (delayed-treatment groups). Specifically, paired t-test or Wilcoxon signed rank test will be used to determine change at 6 or 12 months and this test will be applied to each behavioral test measure separately. False discovery rate will be used to adjust the p-values for multiple hypotheses testing. All statistical analyses will be two sided and the significance level will be 0.05.

Secondary Analyses – For longitudinal analysis, the data will be modeled using linear-mixed models for which the outcome is the behavioral test measure across time. The predictors will include time, group and interaction between group and time. Covariates will be added to the model as needed. In addition, variables with a high Gini score from Part 1 will be correlated with final hearing aid results as a preliminary investigation of whether hearing aid benefit can be associated by any of the variables obtained above. We will measure correlations using either Pearson's or Spearman's correlation coefficient. We will adjust the p-values for multiple testing by using a false discovery rate method whenever more than one variable is being tested. Single-subject design metric also will be used to investigate individual responses to the hearing aid treatment.

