Sample Size and Power – This analysis will include data from 100 participants (25 for each group). For any comparisons of the four groups based on ANOVA with a significance level of 0.01 to account for multiple comparisons and a power of 0.80, an effect size of 0.38 or greater will be detectable. For the paired analyses described above, there is sufficient power (0.80) to detect an effect size of 0.50 (baseline versus 6 months) or 0.50 (baseline versus 12 months), or greater assuming a two-sided significance level of 0.01 to account for multiple comparisons. For the longitudinal modeling, there will be sufficient sample size to support the proposed modeling that will allow approximately 10 observations to be estimated for each parameter. The number of covariates in each model will depend on the sample size to insure that there are approximately 10 observations available for each parameter estimated. For correlation

based analyses, the study is powered (0.80) to detect correlations of 0.26 or greater in absolute value for a total sample size of 100.

Once the data are formatted and cleaned by a staff member at the VA Pittsburgh site under the supervision of the statistician, the data will be analyzed by the statistician.

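### The PTSD half of question e has no planned analysis: the plan gives one simple correlation powered on all 100 participants, without a PTSD term

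*Combined protocol and SAP*

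**What the plan says.** Section 3.0 (Specific Questions, e) asks whether benefit can be predicted from the test measures and then adds: "Furthermore, does the coexistence of PTSD influence the relationship between these measures and hearing aid benefit".

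Section 5.6, Part 2, Secondary Analyses, gives the matching analysis: "variables with a high Gini score from Part 1 will be correlated with final hearing aid results as a preliminary investigation". On method it says: "We will measure correlations using either Pearson's or Spearman's correlation coefficient". Multiplicity is covered by "We will adjust the p-values for multiple testing by using a false discovery rate method whenever more than one variable is being tested".

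The Part 2 power paragraph states, for correlations: "based analyses, the study is powered (0.80) to detect correlations of 0.26 or greater in absolute value for a total sample size of 100". It gives no significance level of its own. The general Part 2 rule is "All statistical analyses will be two sided and the significance level will be 0.05".

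The same section also plans a linear mixed model with time, group and their product, and covariates if needed. Its outcome is the behavioral test measure over time.

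Section 5.2 (Part 2) describes four groups of 25, with a treatment and a delayed-treatment group in each PTSD stratum, and says "the participants from the mTBI-only and mTBI+PTSD groups will be randomly assigned to receive either treatment or delayed treatment". Section 5.1 (Delayed-Treatment Control Group) instead draws the delayed group from the mTBI-only participants alone.

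**The concern.** The second half of question e is a moderation question: does the predictor-benefit relationship differ between mTBI-only and mTBI+PTSD? One correlation over both strata cannot show that. The mixed model does not fill the gap. It can show whether groups change differently over time, which bears on question d, but it contains no predictor-by-PTSD term. If the plan is followed exactly, a stated research question gets no result.

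There is also a matter of interpretation. The Expected Outcomes in section 3.0 say that PTSD will worsen deficits and limit perceived benefit, so PTSD may shift both variables being correlated. The pooled r then combines the difference between strata with the association inside them. It could appear with no within-stratum link, or shrink when a link exists. The second case is plausible if larger deficits go with more benefit while PTSD worsens deficits and lowers benefit. The protocol expects benefit to relate to deficits but gives no direction.

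**Working it through.** **Inputs from the documents.** N = 100 in four groups of 25; two-sided 0.05; power 0.80; stated detectable |r| = 0.26. Section 5.2 gives a 50 v 50 split by PTSD. The documents give no size for the PTSD shifts, so these are assumed and shown as a range.

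**1. The plan's own figure.** By Fisher z, detectable r = tanh[(1.960 + 0.842)/√97] = tanh(0.284) = 0.277. A noncentral t calculation gives 0.272. Power at r = 0.26 is Φ(0.266 × 9.849 − 1.960) = Φ(0.661) = 75%. The stated 0.26 is therefore slightly optimistic at two-sided 0.05 and is worth rechecking when the paragraph is edited. The present point does not depend on it.

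**2. What pooling does.** For two equal strata with within-stratum correlation r_w and PTSD shifts d_x and d_y in within-stratum SDs:

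r_pooled = (r_w + d_x·d_y/4) / √[(1 + d_x²/4)(1 + d_y²/4)]

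The rejection rate is Φ(δ − 1.96) + Φ(−δ − 1.96), with δ = atanh(r_pooled) × √97, at unadjusted two-sided 0.05.

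| Assumed shift on both (SD) | r_w = 0, same direction: pooled r | Rejection rate | r_w = 0.26, opposing directions: pooled r | Power |
|---|---|---|---|---|
| 0.3 | 0.02 | 6% | 0.23 | 64% |
| 0.5 | 0.06 | 9% | 0.19 | 46% |
| 0.8 | 0.14 | 28% | 0.09 | 14% |
| 1.0 | 0.20 | 51% | 0.01 | 5% |

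Example at 0.8 SD: (0 + 0.16)/1.16 = 0.138, and (0.26 − 0.16)/1.16 = 0.086.

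**3. What a moderation test could detect.** For two independent correlations, the detectable Fisher-z difference is q = (1.960 + 0.842) × √[1/(n₁ − 3) + 1/(n₂ − 3)].

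- 50 v 50: SE = √(2/47) = 0.206 and q = 0.58, which is r = 0 v 0.52, or −0.28 v +0.28.
- 25 v 75 (the delayed groups drawn only from mTBI-only, total held at 100): SE = √(1/22 + 1/72) = 0.244 and q = 0.68, which is r = 0 v 0.59.
- Power for r = 0 v 0.26 at 50 v 50: 0.266/0.206 = 1.29, and Φ(1.29 − 1.96) is about 25%. Reaching 80% would take 2 × (2.802/0.266)² + 3, or about 225 per stratum.

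These figures compare correlations. They approximate the slope interaction in a linear model when the SDs are similar across strata.

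**The case against.** The plan is silent on a PTSD-specific correlation but does not forbid one. The analysis is secondary and labelled preliminary, in a part that the protocol says is not a randomized controlled trial. That limits the weight of the point, but a stated question still has no analysis.

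Several stronger readings are tempting, and the documents do not support them.

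- **That question e cannot be answered.** This is true of the plan as written, not of the data. PTSD group is known for every participant.
- **That the pooled correlation is confounded and should be replaced.** The first half of e is about prediction. If PTSD lowers both score and benefit, the score does predict benefit in this mixed population, and the pooled r describes that correctly. It misleads only if read as a link independent of PTSD, which the plan does not claim.
- **That omitting arm biases the correlation.** Section 5.2 assigns arm at random among participants from the two mTBI groups, so Part 1 scores are unrelated to arm in expectation. Arm can add precision only.
- **That false signals are common.** The high rates need shifts near 0.8 to 1.0 SD on both variables and an unadjusted 0.05. At 0.01, the level used elsewhere in the Part 2 power paragraph, they fall to about 11% (Φ(1.367 − 2.576)) and 28% (Φ(1.997 − 2.576)). Multiplicity adjustment makes rejection rarer but leaves the pooled r unchanged. The protocol also expects PTSD to restrict perceived benefit only. It states no such restriction for speech perception or language outcomes.
- **That an interaction test would be well powered.** That holds only for extreme contrasts such as opposite-signed correlations, which nothing in the documents suggests.

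**Conclusion.** The concern holds in a limited form. The second half of question e has no specified analysis, and the power statement covers only one correlation over all 100 participants. This rests on the text alone.

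The mixing of between-group and within-group association is conditional. It needs PTSD to shift both variables. It is slight at 0.3 SD, begins to matter at about 0.5 SD and is substantial at 0.8 SD or more, on assumed shifts and approximately normal data. It calls for an adjusted estimate beside the pooled one.

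The moderation analysis can only be exploratory at this sample size. At 50 v 50, a 95% interval for the Fisher-z difference extends about 1.96 × 0.206 = 0.40 either side. This is a worthwhile and inexpensive correction, not a threat to the study's main conclusions.

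**What to change.** 1. **Section 5.6, Part 2, Secondary Analyses.** Keep the pooled correlation as the description of overall predictability. For each selected predictor, add a linear model (on ranks if non-normal) of the benefit score on predictor, PTSD group, arm (for precision) and predictor-by-PTSD. Report the PTSD-adjusted slope, and the interaction estimate with its confidence interval as an exploratory answer to the second half of question e. Keep the existing false discovery rate adjustment.
2. **Section 5.6, Part 2, Sample Size and Power.** State that at 50 v 50 and two-sided 0.05, 80% power needs a Fisher-z difference of about 0.58 (r = 0 v 0.52), and that power for 0 v 0.26 is about 25%.
3. **Sections 5.1 and 5.2.** Reconcile whether the delayed-treatment group includes mTBI+PTSD participants. A 25 v 75 split would move the detectable difference to about 0 v 0.59.

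The cost is SAP wording, one model per predictor, a few degrees of freedom and a stated power less favourable than the pooled figure. No new data are needed, because PTSD group and arm are already recorded.

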5.6 Data Analysis

Part 1 Analysis

Preliminary Analyses - The analysis will begin with basic descriptive statistics including means and standard deviations for continuous data and examination of distributional assumptions for all study measurements including the questionnaire data (e.g., HHIA, WHODAS-II, SSQ and HHIA-SO) for each group of interest. These analyses will be used to evaluate the extent of missing data and to identify outliers.

Primary Analyses - Random Forests (RF, Breiman, 2001) will be applied to determine which auditory, language processing, and executive function variables best discriminate the three groups. This technique performs variable selection and the variables are ranked by Gini score, a measurement of average accuracy of all trees containing a particular variable. One-way ANOVA will be used to determine differences between groups for normally distributed continuous data. Analysis of covariance (ANCOVA) will be used to adjust for differences between groups. If assumptions for the parametric test are not met, a non-parametric alternative will be used (e.g., Kruskal-Wallis, non-parametric ANCOVA). The p-values will be adjusted for multiple testing by using a false discovery rate method whenever more than one variable is being tested. Statistical assumptions (e.g., linearity, normality) will be verified prior to hypothesis testing. All statistical analyses will be two sided and the significance level will be 0.05.

Sample Size and Power - A sample size of 117 per veteran group will achieve 80% power at a 0.05 significant level to detect an effect size (i.e., odds ratio) of 2.50. This sample size was computed based on an adjustment that was made assuming that a multiple regression of the independent variable of interest on the other independent

variables in the model will result in an R-squared of 0.20. For one-way ANOVA, the total sample of 468 subjects achieves 80% power to detect an effect size of 0.18 or larger with a two-sided significance of 0.01 to account for multiple hypotheses testing. For analysis of covariance, the study is powered (0.80) to detect an effect size of 0.16 assuming the strength of the relationship between the response of interest and the covariates, measured as R-squared, is 0.20.

Part 2 Analysis

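### Part 2's detectable correlation should read about 0.28, not 0.26, for 100 participants at two-sided 0.05 and 80% power

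*Combined protocol and SAP*

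**What the plan says.** Section 5.6, Part 2, Secondary Analyses, plans that "variables with a high Gini score from Part 1 will be correlated with final hearing aid results", to explore whether benefit from the hearing aids can be predicted (question e in section 3.0). It adds: "We will measure correlations using either Pearson's or Spearman's correlation coefficient". On multiplicity it says: "We will adjust the p-values for multiple testing by using a false discovery rate method whenever more than one variable is being tested".

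The Part 2 Sample Size and Power paragraph then states that "the study is powered (0.80) to detect correlations of 0.26 or greater in absolute value for a total sample size of 100". No significance level is attached to that statement. The Part 2 Primary Analyses paragraph supplies the general rule: "All statistical analyses will be two sided and the significance level will be 0.05". The ANOVA and paired-test statements in the same power paragraph use 0.01 instead.

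The ANOVA statement there says that, for four groups at a level of 0.01 and "a power of 0.80, an effect size of 0.38 or greater will be detectable". It does not say which effect-size measure the 0.38 is.

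**The concern.** Sample size, power and significance level together fix the smallest correlation that can be detected. Here the first two are in the sentence and the third is in the general Part 2 rule, so the 0.26 can be checked directly. It is too small for 100 participants, which means the sentence claims more sensitivity than the design has.

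This is the plan's only statement of the size of association that Part 2 can detect for question e. If the correlations come out null, a reader will use it to judge which associations were reasonably ruled out. The missing significance level adds to the difficulty, because the surrounding text uses both 0.05 and 0.01.

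**Working it through.** **Inputs.** N = 100 and power 0.80 come from the correlation sentence. Two-sided 0.05 comes from the general Part 2 rule. The normal quantiles are 1.960 (two-sided 0.05) and 0.842 (80% power).

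**Detectable correlation, Fisher z.**

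r = tanh[(z_α + z_power) / √(N − 3)] = tanh[(1.960 + 0.842) / √97] = tanh(2.802 / 9.849) = tanh(0.2845) = 0.277.

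The stated 0.26 is not reproduced.

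**Power at 0.26.** atanh(0.26) × √97 = 0.2661 × 9.849 = 2.621. Then Φ(2.621 − 1.960) = Φ(0.661) = 0.746.

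**N for 80% power at 0.26.** N = (2.802 / 0.2661)² + 3 = 113.8, so 114.

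**Other methods, two-sided 0.05.**

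| Method | Detectable r | Power at 0.26 |
|---|---|---|
| Fisher z | 0.277 | 74.6% |
| Fisher z, bias-corrected, t critical value | 0.276 | 74.9% |
| Exact, bivariate normal | 0.276 | 75.0% |
| Noncentral t, fixed predictor | 0.272 | 76.0% |

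The noncentral t is the most favourable. It still rounds to 0.27, and it needs N = 111 for 80% power at 0.26. A bivariate-normal simulation with 200,000 repetitions gave power of 74.9% at 0.26 and 81.1% at 0.28.

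**Other significance levels.** The range covers the methods above.

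| Level | Detectable r | Power at 0.26 |
|---|---|---|
| Two-sided 0.01 | 0.328 to 0.334 | 52% to 53% |
| One-sided 0.05 | 0.243 to 0.247 | 84% to 85% |
| One-sided 0.01 | 0.306 to 0.311 | 62% to 63% |

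None gives 0.26. Working backwards by Fisher z, the critical value would have to be 2.621 − 0.842 = 1.779, which is a two-sided level of about 0.075. The plan states no such level.

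**Spearman's coefficient.** This is an approximation that assumes the Fisher z variance is inflated by a factor of 1.034 (1 + r²/2 at r = 0.26) or 1.06. The detectable value is then tanh(0.2845 × √1.034) = 0.281 or tanh(0.2845 × √1.06) = 0.285. The false discovery rate adjustment is not in any of these figures and could only raise the detectable value.

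**ANOVA figure (clarification only).** For four groups of 25 at 0.01, with the noncentral F and noncentrality f² × N, 80% power is reached at Cohen's f = 0.405. As eta this is f / √(1 + f²) = 0.405 / √1.164 = 0.375. Power at 0.38 is therefore 72.9% if it is f and 81.5% if it is eta. The Part 1 ANOVA sentence does not settle which was meant: it says that "the total sample of 468 subjects achieves 80% power to detect an effect size of 0.18 or larger with a two-sided significance of 0.01", and the detectable values there are f = 0.183 and eta = 0.180, both of which round to 0.18.

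**The case against.** The strongest reply is that very little depends on this figure. The gap is 0.26 against 0.272 to 0.277, or four to five points of power. The correlations are a secondary analysis labelled preliminary, and section 5.2 describes Part 2 as preliminary and not a randomized controlled trial. Nothing shows that 100 was chosen to detect 0.26, and no test, enrolment target or decision rule uses it. All of this stands and is why the point is minor.

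A second reply is that the 0.05 is carried over from the general rule, since the correlation sentence states no level. That is true, but it does not rescue the number. The other level used in the paragraph, 0.01, moves the detectable value to about 0.33, further from 0.26.

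A third reply is that planning at an unadjusted level is ordinary practice when the number of tests under a false discovery rate procedure is not yet known. That is fair. The mismatch is shown at the unadjusted level and does not depend on the adjustment or on Spearman's coefficient.

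Finally, the ANOVA figure is not shown to be wrong. Read as eta, 0.38 is correct to rounding. Part 1's 0.18 leans slightly the same way, with power of 80.1% as eta and 78.3% as f. The request there is only to name the measure.

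**Conclusion.** The concern holds. With 100 participants, 80% power and two-sided 0.05, the detectable correlation is about 0.28. At 0.26 the power is about 75%, which is four to five points short, and 80% would need 11 to 14 more participants.

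This rests on applying the general Part 2 level to the correlation sentence, on complete data from all 100 participants, and on no multiplicity adjustment. Spearman's coefficient, missing data or the planned adjustment would each push the detectable value up. Severity is minor: the stated sensitivity is too optimistic, but no design decision follows from it. The ANOVA remark is a request for a label, not a finding of error.

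**What to change.** In the Part 2 Sample Size and Power paragraph, change the detectable correlation to 0.28 and state in the same sentence that the level is two-sided 0.05, before false discovery rate adjustment. If two-sided 0.01 was meant, as in the neighbouring sentences, state that level and about 0.33 instead.

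In the ANOVA sentence, name the effect-size measure. If it is eta, keep 0.38 and label it. If it is Cohen's f, replace 0.38 with 0.41.

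The cost is an edit to two sentences. Enrolment, tests and decision rules do not change.
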